### **7.2.2 Post-Study Reporting Requirements**

All AEs and SAEs including deaths, regardless of cause or relationship, must be reported for subjects on study (including any protocol-required post-treatment follow-up).

Investigators are not obligated to actively seek AEs or SAEs beyond study discharge for subjects. However, if the investigator learns of an AE or SAE that occurs after the completion or termination visit and the event is deemed by the investigator to be probably or possibly related to the Study Treatment, he/she should promptly document and report the event to Inovio Pharmaceuticals.

## **7.3 Methods and Timing of the Collection and Recording of Safety Data**

After study treatment/EP: Study subjects will be directly observed by study personnel for 30-45 minutes after each administration of study treatment/EP for immediate reactions. Injection sites will also be assessed at the subsequent study visit.

The occurrence and severity of any AE during this period or the lack of same will be recorded on the appropriate CRF. Subjects will be given an oral thermometer and instructed to take and record their temperature daily (at the same time each day).

Days 0-3 following study treatment/EP: Subjects will also be instructed to record local and systemic events in a PRC for 3 days following treatment visit as shown in Appendix 9.

Throughout the Study: Subjects will also be queried regarding the occurrence of any possible adverse events, concomitant medications and new onset chronic disease during their clinic visits. Subjects will be reminded to contact study personnel and immediately report any event that may happen for the duration of the study. These events will be recorded on the subject’s CRF.

---

At specified visit the Acute Radiation Morbidity Scoring Criteria (RTOG) form will be completed for each patient to assess systemic reaction/toxicity/side effects of standard (chemoradiation) therapy.

On study treatment/EP visits, the assessments will be performed prior to dosing. Study subjects will be queried at each clinic visit regarding the occurrence of any AEs, including SAEs that may have occurred since the last visit. They will be reminded to contact study personnel and immediately report any such event that happens during the course of the study. These events will be recorded on the CRFs.

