#### **6.2.4.4 Participant Reminder Card**

Subjects will be given an oral thermometer and participant reminder card (PRC) at each study treatment/EP visit. Subjects will be instructed to take and record their temperature daily (at the same time each day). They will also be advised to record local and systemic events on a PRC as shown in Appendix 9.

If Weeks 2, 6, 10 and 12 visits are conducted by telephone, the subject should submit their PRC (i.e. mail, fax, email) to the site personnel prior to the phone visit. If the PRC is not received in advance, site personnel should verbally review all PRC elements listed above. The hard copy of the PRC should be collected at the next in-person study visit. Any entry on PRC determined to meet the criteria for a Grade 1 or higher adverse event should be documented as adverse event. If the PRC entry does not meet the criteria of a Grade 1 or higher AE as per the CTCAE v4.0, clinical judgment can be used to determine whether the entry should be recorded as an AE. For cases where the PRC entry and final AE reporting (i.e., grading) do not agree, the reasoning should be recorded in the source documents.

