### 7.5.2 Events Requiring Expedited Reporting

Events requiring expedited reporting (ERER) will be defined as treatment- or EP-related adverse events including any of the following:

- Grade 3 or greater injection site pain, tenderness, erythema, and/or induration recorded  $\geq 1$  hour after study treatment (see Table 6.1)
- Grade 3 or greater fever assessed by the Principal Investigator as possibly, probably or definitely related to study treatment
- Grade 3 or greater systemic symptoms assessed by the Principal Investigator as possibly, probably or definitely related to study treatment

as defined in the “Common Terminology Criteria for Adverse Events (CTCAE)”, version 4.03 issued by the US Department of Health and Human Services on June 14, 2010 (Appendix 4). The worse grade for that particular event is to be documented on the CRFs.

Sites should inform the Sponsor of any ERER within 72 hours to discuss whether further dosing should continue for that participant.

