Definition: A disorder characterized by a state of generalized weakness with a pronounced inability to summon sufficient energy to accomplish daily activities.					
Fever	38.0 - 39.0 degrees C (100.4 - 102.2 degrees F)	>39.0 - 40.0 degrees C (102.3 - 104.0 degrees F)	>40.0 degrees C (>104.0 degrees F) for <=24 hrs	>40.0 degrees C (>104.0 degrees F) for >24 hrs	Death
Definition: A disorder characterized by elevation of the body's temperature above the upper limit of normal.					
Flu like symptoms	Mild flu-like symptoms present	Moderate symptoms; limiting instrumental ADL	Severe symptoms; limiting self care ADL	-	-
Definition: A disorder characterized by a group of symptoms similar to those observed in patients with the flu. It includes fever, chills, body aches, malaise, loss of appetite and dry cough.					
Gait disturbance	Mild change in gait (e.g., wide-based, limping or hobbling)	Moderate change in gait (e.g., wide-based, limping or hobbling); assistive device indicated; limiting instrumental ADL	Disabling; limiting self care ADL	-	-
Definition: A disorder characterized by walking difficulties.					
Hypothermia	-	35 - >32 degrees C; 95 - >89.6 degrees F	32 - >28 degrees C; 89.6 - >82.4 degrees F	<=28 degrees C; 82.4 degrees F; life-threatening consequences (e.g., coma, hypotension, pulmonary edema, acidemia, ventricular fibrillation)	Death
Definition: A disorder characterized by an abnormally low body temperature. Treatment is required when the body temperature is 35C (95F) or below.					

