### **13.9 Appendix 9: Participant Reminder Card**

## Appendix 10. Participant Reminder Card

Participant ID: \_\_\_\_\_ Date of Study Treatment \_\_\_\_\_

Site of Injection:     Right Arm    Left Arm    Right Leg    Left Leg

**Instructions:** Please complete this reminder card in the evening after and for three days following your study treatment. The “Evening of study treatment” column should include any side effects from the time you received the study treatment until 11:59pm of that day. Days 1, 2 and 3 should include any side effects from midnight (12:00 am) to 11:59 pm of that day (1 day, 2 days or 3 days after receiving the study treatment).

Take this card with you to your next study visit for review with the study team. If you have any questions, or if you have any concerns or side effects that you’d like to discuss, please contact your study team.

To describe the size of any area that is red or swollen, please use the measuring tool provided with this reminder card to indicate the approximate size of a circle that could fully cover the area of redness or swelling.

Possible side effects	Evening of study treatment	1 day after study treatment	2 days after study treatment	3 days after study treatment	Date Resolved
Redness or bruising at treatment site	 None  Diameter (in cm) from measuring tool: _____  Greater than 7cm	 None  Diameter (in cm) from measuring tool: _____  Greater than 7cm	 None  Diameter (in cm) from measuring tool: _____  Greater than 7cm	 None  Diameter (in cm) from measuring tool: _____  Greater than 7cm	<hr/> If date unknown:  1 week**  2 weeks**  3 weeks**

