Pain at treatment site	 None  A little, controlled with OTC* meds  A lot, OTC meds didn’t work, prevented normal activity	 None  A little, controlled with OTC* meds  A lot, OTC meds didn’t work, prevented normal activity	 None  A little, controlled with OTC* meds  A lot, OTC meds didn’t work, prevented normal activity	 None  A little, controlled with OTC* meds  A lot, OTC meds didn’t work, prevented normal activity	<hr/> If date unknown:  1 week**  2 weeks**  3 weeks**
Swelling/ Edema at treatment site	 None  Diameter (in cm) from measuring tool: _____  Greater than 7cm	 None  Diameter (in cm) from measuring tool: _____  Greater than 7cm	 None  Diameter (in cm) from measuring tool: _____  Greater than 7cm	 None  Diameter (in cm) from measuring tool: _____  Greater than 7cm	<hr/> If date unknown:  1 week**  2 weeks**  3 weeks**
Oral Temperature	Please record below:  °F _____  °C	Please record below:  °F _____  °C	Please record below:  °F _____  °C	Please record below:  °F _____  °C	

\* OTC – Over the counter analgesics or painkillers such as paracetamol, acetaminophen (e.g. Tylenol®) or ibuprofen (e.g. Advil® or Motrin®).

\*\* After study treatment

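### One oral temperature a day at a fixed time can miss or under-grade short fevers, and the card alone cannot separate Grade 3 from Grade 4 fever

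*Combined protocol and SAP*

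**What the plan says.** Section 7.3 of the protocol supplies an oral thermometer, and subjects are "instructed to take and record their temperature daily (at the same time each day". Section 6.2.4.4 repeats the instruction. The Participant Reminder Card (Appendix 9) says: "Please complete this reminder card in the evening after and for three days following your study treatment". Its temperature row has four columns, one per day, each with a single blank headed "Please record below". There is no field for clock time, the day's highest value or how long the temperature stayed up. The redness, pain and swelling rows have a resolution entry; the temperature row does not.

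Under section 7.5.2 an event requiring expedited reporting (ERER) includes "Grade 3 or greater fever assessed by the Principal Investigator as possibly, probably or definitely related to study treatment". The same section says: "The worse grade for that particular event is to be documented on the CRFs". In Appendix 4 the CTCAE Fever row sets Grade 1 at 38.0 to 39.0 C and Grade 2 above 39.0 and up to 40.0 C. Grade 3 is ">40.0 degrees C (>104.0 degrees F) for <=24 hrs" and Grade 4 is ">40.0 degrees C (>104.0 degrees F) for >24 hrs".

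**The concern.** The grading scale needs a peak and, above 40.0 C, a duration. The scheduled measurement supplies neither: it is a snapshot at one fixed time each day.

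Fever is the only systemic reaction that the card solicits with a measurement. Card entries of Grade 1 or higher become adverse events (section 6.2.4.4), so they count in primary endpoint 1. Related fever of Grade 3 or more is an ERER and counts toward the one-third rule in 7.5.3.1. If that rule's denominator is the subjects treated so far, one ERER among the first three already reaches one third, so one missed event could matter.

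The split between Grade 3 and Grade 4 also carries weight. Section 4.4 treats attributable Grade 4 toxicity differently from Grade 3. Section 7.1.3 labels Grade 4 as potentially life threatening, a category that 7.5.3.2 names, and 7.5.3.4 has its own provision for unexpected related Grade 4 toxicity.

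**Working it through.** The plan gives no figure for fever detection, so there is none to reproduce.

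**Inputs**
- From 7.3 and 6.2.4.4: scheduled readings 24 h apart.
- From Appendix 9: evening of treatment plus three days, so four values per dose; four doses (section 3).
- From Appendix 4: the Fever grades above.
- Assumed, because the documents give no values: episode length d (time continuously above the threshold in question), onset uniform over the day, and the fever rate used in step 5.

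**1. Direction.** Apart from thermometer error, a single reading cannot exceed that day's maximum. The error can only lower the recorded fever grade.

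**2. Chance that an episode is read.** P(read) = min(1, d/24).

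| d (h) | read | missed |
|---|---|---|
| 3 | 12.5% | 87.5% |
| 6 | 25% | 75% |
| 12 | 50% | 50% |
| 18 | 75% | 25% |
| 24 | 100% | 0% |

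The same formula shows under-grading. Take a fever at or above 38.0 C for 20 h, of which 4 h are above 40.0 C. It is read as fever with probability 20/24 = 83%, but as Grade 3 or more with probability 4/24 = 17%. It is therefore recorded below its true grade with probability 16/24 = 67%, and missed with probability 4/24 = 17%.

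**3. Can the 7.5.2 trigger be applied?** Yes. Any value above 40.0 C is Grade 3 or Grade 4 whatever its duration, and the trigger is Grade 3 or greater. What falls is the chance that such a value is recorded.

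**4. Grade 3 or Grade 4?** With m consecutive readings above 40.0 C and lower readings on each side, the duration lies between 24(m−1) and 24(m+1) h. For m = 1 that is just above 0 to just under 48 h, which straddles the 24 h boundary. For a true duration d between 24 and 48 h (Grade 4), P(only one reading above 40.0 C) = (48−d)/24. For 30 h this is 18/24 = 75%; for 36 h it is 12/24 = 50%.

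**5. Illustration for any-grade fever over four doses.** Let p be the per-dose fever probability and s the share captured, with doses independent and no other route of capture. The share of women with a recorded fever is 1−(1−ps)^4.

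| p (assumed) | s = 1 | s = 0.5 (12 h) | s = 0.25 (6 h) |
|---|---|---|---|
| 5% | 1−0.95^4 = 18.5% | 1−0.975^4 = 9.6% | 1−0.9875^4 = 4.9% |
| 10% | 1−0.90^4 = 34.4% | 1−0.95^4 = 18.5% | 1−0.975^4 = 9.6% |
| 20% | 1−0.80^4 = 59.0% | 1−0.90^4 = 34.4% | 1−0.95^4 = 18.5% |

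This table shows only how under-capture carries through to incidence. It predicts nothing about this product.

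**The case against.** A reader might infer that the fever trigger in 7.5.2 cannot be used at all, or that Grade 3 and Grade 4 can never be told apart. The documents support neither. Step 3 disposes of the first. On the second, an episode above 40.0 C lasting more than 24 h within the card period is read at least once, so it is flagged as at least Grade 3. If judged related, it goes to the sponsor within 72 hours (7.5.2), and 4.4 requires a medical monitor and investigator discussion of attributable Grade 3 toxicity. Duration can be asked about then.

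Nor does a fever between two readings have to go down as normal. The card asks about side effects over the whole of each day, has free-text rows with a daily severity, and asks about symptoms not listed or worse than the choices offered. Section 7.3 asks for immediate reports and queries subjects at visits. Section 6.2.4.4 allows the final grade to differ from the card entry, and nothing forbids extra readings. The prior experience in 1.3 and 1.3.2 also suggests few systemic reactions, so real fever rates may be well below 20% per dose.

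All of this stands, and it limits the point to sensitivity and grading precision. It does not remove it. None of these routes asks the subject for a peak temperature, its time or its duration. Clinic observation ends 30 to 45 minutes after dosing. The next visit is about two weeks later (±1 week), and 6.1.2 lets it be a telephone call without vital signs. A duration sought afterwards depends on recall.

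**Conclusion.** The point holds as a weakness in measurement. Scheduled readings can miss or under-grade fevers shorter than 24 hours, and the error always favours the product. This lowers the sensitivity of primary endpoint 1 and of the fever trigger in 7.5.2. The card by itself also cannot place a fever above 40.0 C in Grade 3 or Grade 4 when only one reading exceeds that level, which bears on the Grade 4 provisions in 4.4 and 7.5.3.

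The size depends on assumptions. The miss rates of 75% (6 h) and 50% (12 h) rest on uniform onset and assumed episode lengths, and count scheduled readings only. The range from just above 0 to just under 48 h assumes a continuous episode with lower card readings on both sides. The direction of the error and the missing peak and duration fields depend on neither onset nor episode length. In a small descriptive study this is a modest defect, but worth correcting because correction is cheap.

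**What to change.** In 7.3, 6.2.4.4 and the reminder card, keep the fixed daily reading, which is comparable across subjects, and add:

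- take the temperature whenever feverish or unwell;
- record each day's highest value with its clock time;
- for any fever, record the first and last times at or above 38.0 C and, where it applies, above 40.0 C.

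State in 8.2, and for the purposes of 7.5.2, that fever is graded from the highest value and these times together with any other reported information.

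The cost is protocol and card wording; the thermometer is already supplied. Subjects take a few extra readings, and the reported fever incidence may be higher. No stopping or treatment rule changes.

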#### **7.4 Procedures for Documenting Pregnancy During Study**

Subjects who are pregnant or expect to become pregnant during the course of the study will be excluded from participation in the study. Should a subject become pregnant after enrolling in the study, she will not be given any further treatments with INO-3112. The Investigator will report this event to Inovio Pharmaceuticals, Inc., or its designee, within 24 hours and to the IRB. The Investigator should counsel the participant and discuss risks of continuing with the pregnancy and the possible effects on the fetus. Sites must request the subject's permission to query pregnancy outcome and follow each subject to determine the outcome of the pregnancy. Results will be summarized in the clinical study report (CSR).

Subjects who become pregnant at any point during the study should continue to be followed for safety assessments without receiving further treatments. Procedures that are contraindicated during pregnancy, including additional vaccinations, must not be performed. Investigators should use clinical judgment regarding subsequent study-related blood collection based on the presence or absence of anemia in each subject. Subjects who are not withdrawn should continue to be followed for safety assessments through discharge per protocol.

All pregnancies that occur from the time of first screening procedure through the follow up visits must be reported. Monitoring of the subject and the outcome of the pregnancy should be followed by the investigator. If the end of the pregnancy occurs after the study has been completed, the outcome should be reported directly to Inovio Pharmaceuticals.

#### **7.5 Toxicity Management**

The Sponsor's Medical Monitor will be responsible for the overall safety monitoring of the study.

##### **7.5.1 Criteria for Halting of Study Enrollment**

Study enrollment (enrollment of new subjects) will be halted if there is a report of Grade 3 anaphylaxis from study treatment/EP with INO-3112. The study may resume enrollment after the safety data has been reviewed and deemed safe to continue by the Medical Monitor and Investigator.

---

### 7.5.2 Events Requiring Expedited Reporting

Events requiring expedited reporting (ERER) will be defined as treatment- or EP-related adverse events including any of the following:

- Grade 3 or greater injection site pain, tenderness, erythema, and/or induration recorded  $\geq 1$  hour after study treatment (see Table 6.1)
- Grade 3 or greater fever assessed by the Principal Investigator as possibly, probably or definitely related to study treatment
- Grade 3 or greater systemic symptoms assessed by the Principal Investigator as possibly, probably or definitely related to study treatment

as defined in the “Common Terminology Criteria for Adverse Events (CTCAE)”, version 4.03 issued by the US Department of Health and Human Services on June 14, 2010 (Appendix 4). The worse grade for that particular event is to be documented on the CRFs.

Sites should inform the Sponsor of any ERER within 72 hours to discuss whether further dosing should continue for that participant.

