#### **4.4 Discontinuation/Withdrawal of Study Subjects**

The subject will be considered to have completed the study when she completes all scheduled Study Treatments and follow-up visits or death, whichever occurs first. The discharge visit will be the last follow-up visit. If subject discontinues or is withdrawn at any time after receipt of Study Treatment, the investigator should make every effort to have the subject complete all assessments designated for the discharge visit. The investigator will make every effort to have all scheduled immune assessment blood sample collected as indicated in the Schedule of Events, Table 1 of the Clinical Synopsis. Any adverse events (AEs) present at the time of discontinuation/withdrawal should be followed in accordance with the safety requirements outlined in Section 7.1 – Safety Parameters.

If the subject manifests Grade 4 toxicity attributable to study treatment/EP, she will not receive further study treatment/EP but will be encouraged to continue follow-up safety assessment through study discharge and not discontinue from the study. If a subject manifests Grade 3 toxicity attributable to study treatment/EP, the medical monitor and PI will discuss whether further treatment should be continued for that participant.

Subjects will be discontinued from the study if there is confirmed disease progression or if subject starts new anti-cancer therapy.

The reason for any discontinuation of study treatment should be discussed with the Sponsor's Medical Monitor within 24 hours. The primary reason for the subject discontinuing further study treatments or withdrawal from the study itself should be selected from the following standard categories:

- Adverse Event (Adverse Reaction): Clinical or laboratory events occurred that, in the medical judgment of the investigator for the best interest of the subject, are grounds for discontinuation. This includes serious and non-serious adverse events regardless of relation to study treatment.
- Death: The subject died.
- Withdrawal of Consent: The subject desired to withdraw from further participation in the study in the absence of an investigator-determined medical need to withdraw. If the subject gave a reason for withdrawal, it should be recorded on the Case Report Form (CRF). This reason does not allow for further data collection and should not be selected if follow-up data collection of this subject is anticipated by the subject.

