### 7.2.1 Abnormal Laboratory Value

Laboratory abnormalities are usually not recorded as AEs or SAEs. However, laboratory abnormalities (e.g., serum chemistry, hematology, CPK, urinalysis) independent of the underlying medical condition that require medical or surgical intervention or lead to study treatment interruption or discontinuation must be recorded as an AE, as well as an SAE, if applicable. In addition, laboratory or other abnormal assessments (e.g., electrocardiogram, x-rays, vital signs) that are associated with signs and/or symptoms must be recorded as an AE or SAE if they meet the definition of an AE (or SAE) as described in Sections 7.1.1 and 7.1.2. If the laboratory abnormality is part of a syndrome, record the syndrome or diagnosis (e.g., anemia) not the laboratory result (e.g., decreased hemoglobin).

Any laboratory abnormality that is new in onset or worsened in severity or frequency from the baseline condition and meets one of the following criteria will be recorded as an AE:

- Requires therapeutic intervention or diagnostic tests
- Leads to discontinuation of study treatment
- Has accompanying or inducing symptoms or signs

- Is judged by the investigator as clinically significant

Grade is an essential element of these criteria. Each CTCAE grading term in the current version is a unique representation of a specific event used for medical documentation and scientific analysis and is a single MedDRA Lowest Level Term (LLT).

Investigators are asked to take the CTCAE grading criteria into account when assessing if a laboratory abnormality qualifies as a laboratory AE. Their clinical judgment ultimately determines whether the abnormality in question is “clinically significant (CS)” or “not clinically significant (NCS)” and the severity of the event. CTCAE grading can be used as a reference when making this determination. It is the responsibility of the Investigators to ensure all AEs are accurately reported and graded.

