### 7.5.3 Stopping Rules (Criteria for Pausing of Study)

- 7.5.3.1 If at any time during the study one third (1/3) or more subjects experience an ERER assessed as possibly, probably or definitely related to study treatment, further enrollment and study treatments will be halted immediately until a thorough investigation has been conducted by the Medical Monitor and Principal Investigator.
- 7.5.3.2 After any SAE, potentially life threatening AE or death assessed as possibly, probably or definitely related to study treatment, further enrollment and study treatments will be halted immediately until a thorough investigation has been conducted by the Medical Monitor, Principal Investigator and IRB (if applicable).
- 7.5.3.3 If three or more subjects in this study, experience the same grade 3 or 4 adverse event, assessed as possibly, probably or definitely related to study treatment, further enrollment and study treatments will be halted immediately until a thorough investigation has been conducted by the Medical Monitor and Principal Investigator.
- 7.5.3.4 In the event of any unexpected Grade 4 toxicities, assessed as possibly, probably or definitely related to study treatment, further enrollment and study treatments will be halted immediately until a thorough investigation has been conducted by the Medical Monitor, Principal Investigator and IRB (if applicable).

- 7.5.3.5 The study will be halted for any report of Grade 3 anaphylaxis from immunotherapy/EP with INO-3112 in two or more patients (as graded per “Common Terminology Criteria for Adverse Events (CTCAE)”, version 4.03 issued by the US Department of Health and Human Services on June 14, 2010 (Appendix 4)).

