#### **9.3.2 Study Reporting Period of Serious Adverse Events**

The reporting period for SAEs (without regard to causality) is the entire period following informed consent until the end of the study.

Each AE will be assessed to determine whether it meets seriousness criteria. If the AE is considered serious, the investigator should report this event to Inovio Pharmaceuticals as outlined below and also to the Ethics Committee according to its standard operating procedures.

Expectedness of SAEs will be determined by Inovio Pharmaceuticals using reference safety information specified in the Investigator's Brochure. An event may qualify for expedited reporting to regulatory authorities if it is a SAE, serious adverse drug reaction, or suspected unexpected serious adverse reaction (SUSAR) in line with relevant legislation. All investigators will receive a safety letter notifying them of relevant SUSAR reports. The investigator should notify the Ethics Committee as soon as is practical, of serious events in writing where this is required by local regulatory authorities, and in accordance with the local institutional policy. The investigator should send the initial report to sponsor within 24 hours of becoming aware of the event. At minimum, the initial report should include the following information:

- Event
- Study code
- Subject number, initials and date of birth
- Investigational study product
- Reporter name and contact information

In the case of a "minimum report" (one that is solely comprised of the information bulleted above), a more detailed follow-up report should be sent as soon as more information becomes available but no later than 7 calendar days after the date of the initial report. Each SAE should be followed up until resolution or stabilization and for a reported death, the

---

investigator should provide Inovio Pharmaceuticals and the Ethics Committee with any additional requested information (e.g., autopsy reports and terminal medical reports).

The original SAE form should be kept at the study site. Inovio Pharmaceuticals or its representative will be responsible for determining and in turn, reporting SAEs to regulatory authorities according to the applicable regulatory requirements.

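### Minor: Section 7.5.2 gives sites 72 hours, with no stated start, to report an ERER, although such reports can complete halting counts in 7.5.3 that require an immediate stop

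*Combined protocol and SAP*

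**What the plan says.** Section 7.5.2 defines ERERs as treatment- or EP-related events and names three kinds, each Grade 3 or higher: injection site reactions recorded an hour or more after treatment, fever, and systemic symptoms. The list is introduced by the word *including*. The reporting rule is: "Sites should inform the Sponsor of any ERER within 72 hours to discuss whether further dosing should continue for that participant". No start is given for the clock, and the only stated purpose is the dosing of the woman affected.

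Section 7.5.3 has two counts that such events can complete, each limited to events judged related. Section 7.5.3.1 reads "If at any time during the study one third (1/3) or more subjects experience an ERER". Section 7.5.3.3 reads "If three or more subjects in this study, experience the same grade 3 or 4 adverse event". Either one stops enrollment and dosing immediately, pending investigation.

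Other provisions bear on timing:

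- Section 7.5: "The Sponsor's Medical Monitor will be responsible for the overall safety monitoring of the study".
- Section 9.3.2, for serious adverse events: "The investigator should send the initial report to sponsor within 24 hours of becoming aware of the event".
- Section 4.4, when dosing is stopped for a subject: "The reason for any discontinuation of study treatment should be discussed with the Sponsor's Medical Monitor within 24 hours".
- Section 4.4, for a Grade 3 toxicity attributed to treatment: "the medical monitor and PI will discuss whether further treatment should be continued for that participant". No time limit is set.
- Section 7.2.1 makes a laboratory finding an adverse event under stated conditions, starting from "Any laboratory abnormality that is new in onset or worsened in severity or frequency from the baseline condition". Clinical significance in the investigator's judgment is one of those conditions.

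**The concern.** The Synopsis plans two sites, and the counts run across the study. A stop triggered by a count can take effect only once the completing report has arrived. An immediate stop therefore depends on an input that may take three days. In that time the other site may enroll or dose a woman although a threshold has been met.

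The missing start adds to this. One site could count from onset and the other from awareness or from the causality assessment, and both would comply.

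The scope of 7.5.2 also does not clearly match that of 7.5.3.3. The latter counts any same related Grade 3 or 4 event, including a laboratory one. Whether a related Grade 3 laboratory event is an ERER depends on how open the list in 7.5.2 is.

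**Working it through.** The plan gives no figure on this point to reproduce. The check sets the reporting routes side by side and then sizes the gap.

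**Which events are affected**

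| Related event | Limit | Stated start | Section |
|---|---|---|---|
| Serious | 24 h | site awareness | 9.3.2 |
| Treatment stopped for that woman (required for attributable Grade 4) | 24 h, discussion | none | 4.4 |
| Non-serious Grade 3 site reaction, fever or systemic symptom, treatment continues | 72 h | none | 7.5.2 |
| Non-serious Grade 3 laboratory event, treatment continues | unclear: 72 h if the ERER list is open; otherwise only the discussion in 4.4, with no limit | none | 7.5.2, 4.4 |

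Only the last two rows are in question.

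**What a 24-hour limit from awareness would save.** If the present clock starts at awareness, up to 72 − 24 = 48 hours. If it starts at onset, 24 hours from awareness could fall later than the present limit for an event found late, for example when a reminder card is reviewed at a visit (Section 6.1.2). The gain is then mainly a workable start that both sites share.

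**Size, on the awareness reading.** From the documents: 10 subjects × 4 doses = 40 doses (Section 3), at 2 sites (Synopsis). Assumed, because the documents do not say: 20 of the 40 doses at the other site, spread evenly over T = 365 or 730 days; the reporting site uses its full window; events are independent, with 2%, 5% or 10% of subjects having a related Grade 3 event.

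*Step 1: a count has just been met.* The chance of at least one dose at the other site within d days is 1 − exp(−20 × d / T).

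| T | 72 h (d = 3) | 24 h (d = 1) | Difference |
|---|---|---|---|
| 365 days | 1 − exp(−0.164) = 15.2% | 1 − exp(−0.055) = 5.3% | 9.8 points |
| 730 days | 1 − exp(−0.082) = 7.9% | 1 − exp(−0.027) = 2.7% | 5.2 points |

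With 8 doses at the other site the differences are 4.2 and 2.1 points; with 32 doses, 14.7 and 8.0 points.

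*Step 2: chance that a count is met, with all 10 subjects as denominator.* Section 7.5.3.3 needs three subjects. Section 7.5.3.1 needs four, since 3/10 is below one third. P(at least 3 of 10) therefore bounds both. For 7.5.3.3 it is an upper bound because the event must also be the same one.

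| Rate | P(≥3 of 10) | P(≥4 of 10) |
|---|---|---|
| 2% | 0.09% | 0.003% |
| 5% | 1.15% | 0.10% |
| 10% | 7.02% | 1.28% |

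*Step 3: product.*

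- 2%: 9.8 × 0.0009 = 0.009 points at most.
- 5%: 5.2 × 0.0115 = 0.06 to 9.8 × 0.0115 = 0.11 points.
- 10%: 5.2 × 0.0702 = 0.36 to 9.8 × 0.0702 = 0.69 points.

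With 32 of the 40 doses at the other site, the top figure becomes 14.7 × 0.0702 = 1.03 points. In the other direction, dosing runs 12 weeks past the last Day 0. If 365 days is taken as the accrual period, T becomes 365 + 84 = 449 days and the 72-hour chance falls from 15.2% to 12.5%.

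**The case against.** The best defense is that the clocks are graded by seriousness. Graver events have the faster or harsher rules: 24 hours for serious events, and a halt after a single related serious or potentially life-threatening event (7.5.3.2). A finite 72-hour limit for non-serious events fits that scheme, and nothing in the documents requires 24 hours for them. This stands, and it is why the point is a design choice rather than an error.

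The start of the clock is partly implied. A site reaction must be recorded, and fever or a systemic symptom must be assessed as related, before there is an ERER to report. That narrows the ambiguity, but recording, assessment and awareness can still fall on different days.

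The reports can already serve the counts. They go to the Sponsor, whose Medical Monitor has study-wide responsibility and is named in 7.5.3.1 and 7.5.3.3. The purpose stated in 7.5.2 does not bar other use. This also stands: what is missing is speed, not authority.

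A reader might infer that related Grade 3 laboratory events have no route to the Medical Monitor at all. The documents do not support that. The word *including* can be read as leaving the ERER list open, and 4.4 calls for a discussion of any attributable Grade 3 toxicity. Section 6.2.4.9 also has treatment-visit laboratory results reviewed before dosing, which protects the affected woman's own next dose. Only the timing is open.

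Events may also be rare. Section 1.3.1 reports very few related Grade 3 events after 551 doses of VGX-3100. That experience was without the IL-12 plasmid, so it lowers the expected benefit without settling the rate here.

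**Conclusion.** The point holds as a minor, cheap improvement. A report that may take 72 hours from an undefined start can complete a count that calls for an immediate stop at both sites. It concerns non-serious related Grade 3 events in women who stay on treatment.

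The benefit is small: at most about 0.1 points at a 5% event rate and 0.7 points at 10%, in the chance of one further dose, with all 10 subjects as denominator and an even split of doses. These figures rest on assumed accrual, site split and event rates, on full use of the reporting window, and on the awareness reading of the present clock. The textual mismatch does not depend on them.

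Two stronger readings should be resisted. A reader might infer that 7.5.2 contradicts 7.5.3. It does not: the stop can still be immediate once the count is known. A reader might also infer a larger effect by counting only subjects treated so far in 7.5.3.1, where one ERER among the first three women would reach one third. Section 7.5.3.1 does not state its denominator. That is a separate ambiguity, and few women would be on treatment when so early a count was met, so it is not used to size this point.

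**What to change.** Revise the reporting sentence in 7.5.2 so that sites report any ERER, and any other related Grade 3 or higher adverse event that counts toward 7.5.3.3 (laboratory events included), to the Medical Monitor within 24 hours of becoming aware of it, using the route in Section 9.3.2. It would help to add that the Medical Monitor updates the 7.5.3.1 and 7.5.3.3 counts with each report. The thresholds need no change.

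The cost is a sentence or two of protocol text and a few non-serious reports sent sooner, by up to two days if the present clock starts at awareness. The change does not shorten any delay before the site learns of an event. That still depends on women reporting promptly, as Section 6.4 asks, and on review at later visits.
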